For example, the area shown to the right measures 3 centimeters (cm) because it is touching the 3cm line.

General and Other Symptoms or Medications

If you have additional symptoms that are not listed, or if you sought medical care for any reason from a health care provider (e.g. doctor's office, emergency room), or if you took any medications, these should be listed in the spaces provided. Please designate any symptoms as Mild, Moderate, or Severe.

- Mild I only had minor discomfort. I went about my usual activities.
- Moderate : I noticed the symptom. It bothered me enough that I didn't do as much as I usually do.
- Severe I really noticed the symptom. It kept me from doing something I wanted or had to do.

Day 5: 5 Days After Injec	tion Subject#	i	Date:		
The items on this page refer to the information changes after you fill of	e time between midn out this page but befo	ight of last night and ore 11:59 p.m. tonigh	d 11:59 p.m. today it, make any necess	(Day 5). If sary changes b	any of the below.
Temperature					
	or °F (circle one)	Time Taken:	AM o	r PM (circle o	one)
General Symptoms If you experience any of these sym (Day 5). See General Instruction	s on page 12 for mor	e information.	**************************************		
Symptom	None	Mild	Moderate	_	ere
Unusually tired/feeling unwell					
Muscle aches					 
Headache					
Nausea					
Joint pain					
If you experience an injection site (Day 5). See General Instruction Symptom			Moderate		ere
Pain					
Itching					
	191				
Redness, Swelling, or Bruising	None	Provide	e Maximum Meas	urement	
Redness		(4)	cm at the longest	t part	
Swelling			cm at the longest	part	
Bruising			cm at the longest	part	
Other Symptoms If you experience symptoms other Instructions on page 12. Did you experience any other		13 - 34	ace below according	ng to the Gene	eral
Sympto	om or Medical Ev	ent	Mild	Moderate	Severe
Did you take any medications If yes, please list out the name		pelow:			

Participant Diary HPV-301 Version 1.0 - 10 May 2016

Temperature

Take your temperature orally around the same time each evening, using the thermometer provided and record it in the space provided. Also record the time at which you took your temperature. If you recently drank very hot or cold liquids, wait 15 minutes before taking your temperature.

Injection Site Symptoms

Pain and itching

Some people experience pain in the area where they were injected. Some people may also experience itching in the area where they were injected.

. By pain we mean that the place where you were injected hurts even when it isn't touched.

If you experience pain or itching at the injection site, use the following categories to describe how severe these symptoms were. If you don't experience one or more of these symptoms, mark the NONE box.

- Mild in I only had a little discomfort. I could still use my arm like always.
- Moderate ! I noticed the discomfort and didn't use my arm as much as usual.
- Severe ! I really noticed the discomfort. It kept me from doing something I wanted or had to do.

Redness, swelling, and bruising

Some people experience redness, swelling, or bruising in the area where they were injected. If you experience redness, swelling, or bruising, measure the area using the measuring tool you were provided, and record the measurement in the space provided.

To measure the area of redness, swelling, or bruising, do the following:

- Place the measuring tool over the area where you were injected, with the dot over the center of the area.
- Select the circle where the longest part of the area touches the line.
- If the area is in between two circles, select the larger circle.

For example, the area shown to the right measures 3 centimeters (cm) because it is touching the 3cm line.

General and Other Symptoms or Medications

If you have additional symptoms that are not listed, or if you sought medical care for any reason from a health care provider (e.g. doctor's office, emergency room), or if you took any medications, these should be listed in the spaces provided. Please designate any symptoms as Mild, Moderate, or Severe.

- Mild I only had minor discomfort. I went about my usual activities.
- Moderate ! I noticed the symptom. It bothered me enough that I didn't do as much as I usually do.
- Severe : I really noticed the symptom. It kept me from doing something I wanted or had to do.

Day 6: 6 Days After Inj	ection Subject #	i	Date:		
The items on this page refer to symptoms you reported on prev or Doctor know. Temperature	the time between midnig vious pages have not gon	tht of last night and lee away ("resolved"),	1:59 p.m. today (, you will need to	Day 6). If any let the Site Co	of the ordinator
Evening Temp.:	°C or °F (circle one)	Time Taken:	AM	or PM (circle	one)
General Symptoms If you experience any of these s (Day 6). See General Instruct			worst symptom ur	ntil 11:59 p.m.	tonight
Symptom	None	Mild	Moderate	Sev	vere
Unusually tired/feeling unwel					
Muscle aches				[
Headache					
Nausea				[]
Joint pain				1	
Injection Site Symptoms If you experience an injection s (Day 6). See General Instruct	tions on page 14 for mor	e information.			70.0
Symptom	None	Mild	Moderate		vere
Pain					
Itching					
Dadwara Swalling on Davids	ng None	Dunnid	Maximum Mea		
Redness, Swelling, or Bruisin Redness	Ig None	Provide			
Swelling	+ +		cm at the longer		
Bruising			cm at the longer		
Bruising			_ cm at the longer	st part	
Other Symptoms If you experience symptoms of Instructions on page 14. Did you experience any oth	ner symptoms? 🗌 Ye	s 🗌 No			eral
Sym	iptom or Medical Evo	ent	Mild	Moderate	Severe
Did you take any medication If yes, please list out the na	The state of the s	oelow:			

Participant Diary HPV-301 Version 1.0 - 10 May 2016

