6.4 INJECTION AND ELECTROPORATION (EP)

Subjects will receive a 3-dose series of either 1 ml VGX-3100 or Placebo by IM injection in the deltoid (or anterolateral quadriceps muscle as an alternate option, if deltoid muscle is not possible or appropriate) followed immediately by EP with the CELLECTRA™ 5PSP. Study treatment must not be given within 2 cm of a tattoo, keloid or hypertrophic scar. If there is implanted metal, implanted device, within the same limb then use of the deltoid muscle on the same side of the body is excluded.

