15 APPENDICES

15.1 APPENDIX A: PARTICIPANT DIARY CARD

Subject Diary HPV-301

Subject #:	
Injection Date:	

Note to Participant:

For questions or problems, please contact your Site Coordinator.

Name:	
Telephone: ()	
Email (optional):	

Participant Diary HPV-301 Version 1.0 - 10 May 2016

Temperature

Take your temperature orally around the same time each evening, using the thermometer provided and record it in the space provided. Also record the time at which you took your temperature. If you recently drank very hot or cold liquids, wait 15 minutes before taking your temperature.

Injection Site Symptoms

Pain and itching

Some people experience pain in the area where they were injected. Some people may also experience itching in the area where they were injected.

. By pain we mean that the place where you were injected hurts even when it isn't touched.

If you experience pain or itching at the injection site, use the following categories to describe how severe these symptoms were. If you don't experience one or more of these symptoms, mark the NONE box.

- Mild in I only had a little discomfort. I could still use my arm like always.
- Moderate ! I noticed the discomfort and didn't use my arm as much as usual.
- Severe ! I really noticed the discomfort. It kept me from doing something I wanted or had to do.

Redness, swelling, and bruising

Some people experience redness, swelling, or bruising in the area where they were injected. If you experience redness, swelling, or bruising, measure the area using the measuring tool you were provided, and record the measurement in the space provided.

To measure the area of redness, swelling, or bruising, do the following:

- Place the measuring tool over the area where you were injected, with the dot over the center of the area.
- Select the circle where the longest part of the area touches the line.
- If the area is in between two circles, select the larger circle.

For example, the area shown to the right measures 3 centimeters (cm) because it is touching the 3cm line.

General and Other Symptoms or Medications

If you have additional symptoms that are not listed, or if you sought medical care for any reason from a health care provider (e.g. doctor's office, emergency room), or if you took any medications, these should be listed in the spaces provided. Please designate any symptoms as Mild, Moderate, or Severe.

- Mild I only had minor discomfort. I went about my usual activities.

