- iii. Section 8.9 (Efficacy Analysis) has been revised to add a description regarding the Immunoscore analysis per Exploratory Objective 6.
- iv. Section 8.10 (Immunogenicity Analyses) has additional clarifying information regarding the evaluation of immune assays.
- v. Section 8.11.1 (Adverse Events) has been revised to clarify the use of start and stop dates of adverse events for analysis purposes.
- vi. Section 8.14 (Patient Reported Outcomes) has been revised to change the testing method from non-parametric or Miettinen and Nurminen to Wilcoxon rank-sum test or Pearson chi-square test/Fisher's exact test, which is appropriate for scales with multiple categories rather than only two categories.
- q. Section 9.4.2 (Pathology Adjudication Committee) now refers to the PAC charter, which has the most current information regarding the PAC review process.
- r. The Participant Diary Card is unchanged but has been removed from the Appendix since the Participant Diary Card is a separate document.
- 5. Additional minor grammatical and administrative changes have been made throughout the document for improvement of general readability.

INVESTIGATOR ACKNOWLEDGEMENT

I have read this Protocol and agree that it contains all necessary details for carrying out the study described. I understand that it must be reviewed by the Institutional Review Board or Independent Ethics Committee overseeing the conduct of the study and approved or given favorable opinion before implementation.

The signature of the Investigator below constitute his/her approval of this protocol and provide the necessary assurances that this study will be conducted according to the Declaration of Helsinki, ICH-GCP guidelines, local legal and regulatory requirements as well as to all stipulations of the protocol in both the clinical and administrative sections, including statements regarding confidentiality.

Investigator – Signature	Date (DD/MMM/YYYY)
Investigator – Printed Name	
Site Number:	
Site Name:	

TABLE OF CONTENTS

St	ımma	ry of Changes	3	
In	vestig	ator Acknowledgement	7	
Ta	able o	f Contents	8	
i	List	Of Abbreviations and definitions	13	
ii	Clin	ical Protocol Synopsis	15	
1	Intro	oduction		
	1.1	Background	24	
		1.1.1 HPV Infection, Cervical Intraepithelial Neoplasia and Cervical Cancer	24	
		1.1.2 VGX-3100	25	
		1.1.3 Electroporation	25	
		1.1.4 Selection of study design	26	
	1.2	Dose and Regimen Rationale	27	
	1.3	Risks/Benefit Assessment		

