6.4 INJECTION AND ELECTROPORATION (EP)

Subjects will receive a 3-dose series of either 1 ml VGX-3100 or Placebo by IM injection in the deltoid (or anterolateral quadriceps muscle as an alternate option, if deltoid muscle is not possible or appropriate) followed immediately by EP with the CELLECTRA™ 5PSP. Study treatment must not be given within 2 cm of a tattoo, keloid or hypertrophic scar. If there is implanted metal, implanted device, within the same limb then use of the deltoid muscle on the same side of the body is excluded.

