6.6 ASSESSMENT OF CLINICAL STUDY ADVERSE EVENTS

The injection site will be assessed by study personnel prior to and at least 30 minutes after each study treatment and at 2 to 4 weeks post study treatment visits. They will also be advised to record local and systemic AEs for 7 days on a PDC.

An adverse event assessment will be conducted at each visit during which subjects will be queried regarding the occurrence of any adverse events, concomitant medications new onset illness or disease, as well as contraceptive compliance. Subjects will be reminded to contact study personnel and immediately report any event that happens for the duration of the study. Unsolicited adverse events will be captured from the time of the informed consent to study discharge. These events will be recorded on the subject's CRF.

6.7 ASSESSMENT OF INJECTION SITE REACTIONS

When evaluating injection site reactions throughout the study, the investigator will be instructed to use the following grading scale:

Table 15. Grading Scale for Injection Site Reactions

Local Reaction to Injectable Product (Grade)	Mild(1)	Moderate(2)	Severe(3)	Potentially Life Threatening(4)
Pain	Does not interfere with activity	Repeated use of non- narcotic pain reliever >24 hours or interferes with activity	Any use of narcotic pain reliever or prevents daily activity***	Emergency room (ER) visit or hospitalization
Tenderness	Mild discomfort to touch	Discomfort with movement	Significant discomfort at rest	ER visit or hospitalization
Erythema/Redness*	2.5-5 cm	5.1-10 cm	>10 cm	Necrosis or exfoliative dermatitis
Induration/Swelling**	2.5-5 cm and does not interfere with activity	5.1-10 cm or interferes with activity	>10 cm or prevents daily activity	Necrosis

September 2007 "FDA Guidance for Industry—Toxicity Grading Scale for Healthy Adult and Adolescent Volunteers Enrolled in Preventive Vaccine Clinical Trials"

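### The diary card's Mild and Moderate anchors for injection-site pain and itching refer only to the arm, although thigh injection is allowed, so after a thigh injection no Moderate anchor fits

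*Protocol*

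**What the plan says.** **Diary card.** Appendix A of the older protocol version reproduces the card (diary version 1.0, 10 May 2016). For pain and itching at the injection site, Mild combines slight discomfort with "I could still use my arm like always". Moderate is "I noticed the discomfort and didn't use my arm as much as usual". Severe names no limb: "It kept me from doing something I wanted or had to do". The same instructions are repeated for each diary day.

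**Injection site.** Section 6.4 makes the deltoid the usual site and allows the "anterolateral quadriceps muscle as an alternate option, if deltoid muscle is not possible or appropriate". This text is the same in the older version and in version 5.0. Section 2.2 of version 5.0 calls the deltoid preferred and the quadriceps the alternate. Exclusion criterion 19 counts both muscles when it asks for acceptable sites.

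**Status of the card.** The version 4.0 Summary of Changes, item 4(r), states: "The Participant Diary Card is unchanged but has been removed from the Appendix since the Participant Diary Card is a separate document". The version 5.0 Summary of Changes lists no diary revision.

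**Grading.** Under Section 6.7, for injection-site reactions, "the investigator will be instructed to use the following grading scale" (Table 15 in version 5.0, Table 12 in the older version). Section 7.1.5 of version 5.0 points to the same table. Secondary endpoint 1a is the incidence and severity of local and systemic events over 7 and 28 days after each treatment and over the whole study. The synopsis and Section 2.3 say the 7-day events are monitored through the diary.

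**The concern.** A severity scale completed by the participant works only if each category can apply to every participant who uses it. Here two of the three categories are tied to a limb that an allowed injection does not touch. A woman injected in the thigh can always use her arm normally, whatever her thigh feels like.

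The diary is the day-by-day record of local symptoms in the week after each dose, made when the symptoms occur. If its middle category has no usable anchor for some women, their entries are pushed towards Mild or Severe, or depend on how each woman chooses to reread the text. Staff and investigator then start from that entry when they grade the event for endpoint 1a.

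**Working it through.** The plan states no figure on this point, so the check compares texts.

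**Step 1. The scales side by side (pain).**

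| Level | Diary, injection-site pain and itching | Diary, general symptoms | Investigator scale, Table 15 pain row |
|---|---|---|---|
| Mild / 1 | Slight discomfort, and arm use as normal | Minor discomfort, usual activities kept up | Activity not affected |
| Moderate / 2 | Discomfort noticed, and arm used less | Symptom noticed, and less done than usual | Activity affected, or repeated non-narcotic analgesic for more than 24 hours |
| Severe / 3 | Something wanted or needed was prevented | Something wanted or needed was prevented | Daily activity prevented, or any narcotic analgesic |

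Only the first diary column names a limb, and only in its Mild and Moderate rows. Table 15 has no row for itching, so the comparison with the investigator scale is limited to pain.

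**Step 2. A test case.** Take an injection in the thigh, after which pain makes the woman walk less than usual but prevents nothing she wanted or had to do.

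- Table 15: activity is affected, so Grade 2.
- Diary Mild: normal arm use is true, slight discomfort is not.
- Diary Moderate: discomfort noticed is true, reduced arm use is not.
- Diary Severe: not met, because nothing was prevented.

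No diary category is fully met. The same pain after a deltoid injection, limiting the arm instead of the leg, would meet Moderate in full. The card's own general-symptom wording would also have placed the thigh case in Moderate.

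**Step 3. How a diary entry reaches a recorded grade.** The diary covers the evening of treatment through Day 6. Under Section 6.3.3.10, staff review it with the subject at the call 8 to 14 days after the dose and again at the next in-person visit, so the review comes after the diary week has ended. The investigator assigns the grade. Version 5.0 expects that diary and grade may differ and asks for the reasoning in the source documents. Section 8.11.1 summarises adverse events by maximum severity, including a summary of events within 7 days of a dose. Section 8 of the protocol describes no analysis of raw diary categories.

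**Step 4. How many diaries.** Planned doses are 198 subjects × 3 doses = 594, with one diary per dose. If a share *s* of doses went into the thigh, 594 × *s* diaries would be completed on anchors that do not fit. Each percentage point of *s* would be 594 × 0.01 = 5.94, or about 6 diaries. The documents give no value or range for *s*, so the count stays open. Even 594 × *s* would be too high, because it includes women who had no pain or itching to rate.

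**The case against.** The strongest reply is that the diary does not set the grade. The investigator does, on a scale that names no limb, after going through the diary with the subject, and Section 6.3.3.10 of version 5.0 already provides for disagreement between the two. This stands. A reader might infer from the card that pain after thigh injection is under- or over-graded in the trial data, or that moderate pain is lost. The documents do not support that: pain that limits walking is Grade 2 under Table 15 whatever box was ticked. What remains is a risk of carry-over, because the only daily record is the woman's own and the review happens afterwards.

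Second, the full Mild anchor also requires only slight discomfort, so pain that limits walking does not drop cleanly into Mild. This also stands. It means that no category fits, not that the rating is always too low. A sensible participant may read the arm as meaning the injected limb, or ask the site coordinator as the card invites, but the instrument should not depend on that.

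Third, the quoted page sits in a superseded appendix, and the card used under version 5.0 is not shown. This is a fair limit. Continued use is inferred from the version 4.0 statement and from the absence of any diary item in the version 5.0 change list.

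Fourth, the thigh is only the fallback site, so few diaries may be affected. That is plausible, but the documents give no figure either way.

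**Conclusion.** The mismatch is real and minor. An allowed injection site has no Moderate anchor that fits, so the diary self-rating of pain and itching after a thigh injection can be misclassified, and this may influence the investigator's grade for endpoint 1a.

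Its limits are clear:

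- The recorded grade is the investigator's.
- The card and the site rule are the same in both blinded arms, so no between-arm bias is shown. Any effect would be on the absolute severity profile.
- The special-interest criterion for site pain (Section 7.3.1) starts at Grade 4, well above the Mild/Moderate boundary. The pausing rules in Section 7.3.2 that turn on a grade use events verified against protocol definitions, not diary categories.
- The number of affected diaries cannot be estimated from the documents.

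The conclusion assumes that the card's wording has not changed since the version 4.0 statement and that some doses are given in the thigh. It is a cheap improvement, not a threat to any analysis.

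**What to change.** In the Mild and Moderate anchors for injection-site pain and itching, replace *my arm* with *the arm or leg that was injected*, on every instruction page of the card. The Severe anchor needs no change. For deltoid injections the scale keeps its meaning, and no dose, site rule or grading rule is touched.

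The cost is a reprint of the card. The downside is two card wordings within the trial, so the card version in use should be identifiable for each dose. If the card now in use already has limb-neutral wording, no action is needed beyond confirming it.

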6.3.3.10 Subject Self Evaluation

Subjects will be provided a PDC and will be asked to record the following the evening of study treatment through Day 6:

- Oral temperature and time taken (before 11:59 pm)
- General symptoms of feeling unwell
- Pain and itching at injection site
- Measure redness, swelling, bruising at injection site
- Medications taken

The completed PDC will be reviewed with the subject by the study staff at 8 -14 days post-dose phone call and next in-person visit.

The study staff will review the PDC for general symptoms (e.g. malaise, fatigue, headache, nausea, and myalgia/arthralgia), injection site reaction symptoms (e.g. pain, erythema and edema), medical events and medications.

Any PDC entry determined to meet the CTCAE criteria for a Grade 1 or higher adverse event should be documented as an adverse event unless deemed part of the subject's ongoing medical history. If the PDC entry does not meet the criteria of a Grade 1 or higher AE as per the CTCAE guidelines, clinical judgment can be used to determine whether the entry should be recorded as an AE and documented accordingly in the site's source. For cases where the PDC entry and final AE reporting (i.e. grading) do not agree, the reasoning should be recorded in the source documents.

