6.8 ASSESSMENT OF PATIENT REPORTED OUTCOMES

To assess quality of life and related impacts on subjects, two previously-validated patient-reported outcomes (PRO) instruments will be provided to the subjects enrolled in US, Canada, Mexico, UK and Germany. The following two PRO questionnaires will be used:

- 1. Short Form Health Survey, **version 2** (**SF-36v2[™]**) (Optum, Inc.): generically measures functional health and well-being, for physical and mental health; consists of thirty-six items covering eight domains (Physical functioning, Role limitations due to physical problems, Bodily pain, General health, Vitality, Social functioning, Role limitations due to emotional problems, and Mental health) [26]
- 2. **EQ-5D-5L** (EuroQol Research Foundation): generically measures activities & general health status; consists of six items covering six domains (Mobility, Self-care, Usual activity, Pain/discomfort, Anxiety/depression, and Global health status) [27, 28]

Either one or both PRO instruments (refer to Section 6.2) will be provided to the subject who will be instructed to complete the questionnaire at the following time points:

- Day 0 (*before* the first study treatment)
- 8-14 days post dose 1
- Week 4 (after study treatment)
- 8-14 days post dose 2
- Week 12 (after study treatment)

^{*}In addition to grading the measured local reaction at the greatest single diameter, the measurement should be recorded as a continuous variable

^{**}Induration/Swelling should be evaluated and graded using the functional scale as well as the actual measurement
*** Sponsor defines daily as impact lasting > 24 hours

- 8-14 days post dose 3
- 8 -14 days post Week 28
- Week 36 (after biopsy or surgical excision)
- 8-14 days post Week 40
- Week 88

Administration of PRO instruments will be performed according to the validated procedure and guidelines of each respective instrument, except for some assessments for exploratory analyses. Additional instructions will be provided separately.

Additional questions related to the subject's quality of life following surgery or biopsy will be completed at the Week 40 phone call for subjects enrolled in USA, Canada, Mexico, UK and Germany.

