7.3.1 ADVERSE EVENTS OF SPECIAL INTEREST

Adverse events of special interest (AESI) are the adverse events deemed related to VGX-3100/placebo delivered with CELLECTRA[™] 5PSP that require expedited communication from the Site to the Sponsor and meet any of the following criteria:

- Grade 3 or greater persistent administration site erythema, and/or induration recorded ≥ 2 hours immediately after Study Treatment
- Grade 4 or greater persistent administration site pain, tenderness recorded ≥ 2 hours immediately after Study Treatment
- Grade 3 or greater fever
- Grade 3 or greater systemic symptoms, including generalized pruritus

Sites will inform the Sponsor via method described in section 7.4.1 within 24 hours to discuss whether further dosing for the particular subject should continue.

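### The diary card records swelling by size only, although the grading table also grades it by effect on activity, so that half of the grade rests on unprompted recall and can come out too low

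*Protocol*

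**What the plan says.** The diary card is reproduced as Appendix A of the earliest protocol version in the file. For redness, swelling and bruising it asks for a length: "If you experience redness, swelling, or bruising, measure the area using the measuring tool you were provided", and then "Select the circle where the longest part of the area touches the line". Each daily page offers a box for none and a space for centimetres. Pain and itching are handled differently, with mild, moderate and severe boxes worded by use of the arm; the moderate level reads "I noticed the discomfort and didn't use my arm as much as usual". General symptoms have similar boxes.

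Section 6.3.3.10 lists what the subject records, and its entry for these signs is "Measure redness, swelling, bruising at injection site".

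The grading table in Section 6.7 sets Grade 3 for induration/swelling at ">10 cm or prevents daily activity". Grade 2 is likewise a size band or interference with activity, and Grade 1 requires that there be no interference. A footnote states: "Induration/Swelling should be evaluated and graded using the functional scale as well as the actual measurement". The swelling row and this footnote are the same in Table 12 and Table 15.

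Section 7.3.1 lists among the events of special interest "Grade 3 or greater persistent administration site erythema, and/or induration recorded" at 2 hours or more after treatment. Pain and tenderness qualify only at Grade 4.

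On versions, the version 4.0 summary of changes says "The Participant Diary Card is unchanged" and removes the card from the appendix as a separate document. The version 5.0 change list mentions no diary change, but the card used under that version is not shown.

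**The concern.** Secondary endpoint 1a is the incidence and severity of local and systemic events for 7 and 28 days after each treatment and for the whole study. The diary is the only daily record in the first week. For swelling, one of the two criteria that set the grade is not collected on the day it applies.

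The timing matters. Site staff examine the injection site at least 30 minutes after treatment. The next planned contact is the call at 8 to 14 days, by which time a short-lived limitation may be over. Section 6.3.3.10 tells staff to review the diary for injection-site symptoms but gives no functional question for swelling.

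At stake are the severity distribution of local reactions and the detection of an event of special interest in an individual subject. Such an event triggers a report to the sponsor within 24 hours and a discussion of that subject's further dosing. The pain item cannot stand in for it: a limitation recorded as Grade 3 pain is not an event of special interest, whereas the same limitation attributed to swelling meets the grade.

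**Working it through.** The plan states no figure on this point, so there is none to reproduce. The check compares the grade obtainable from the diary entry alone with the grade the table requires.

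**Inputs** (Section 6.7, induration/swelling row; Grade 4 is necrosis and is not in question):
- Size grade S: below 2.5 cm = 0; 2.5 to 5 cm = 1; 5.1 to 10 cm = 2; above 10 cm = 3.
- Functional grade F: no interference = 0 (adds nothing to the size grade); interferes = 2; prevents daily activity = 3.
- Because Grades 2 and 3 are joined by *or*, table grade = max(S, F).
- The diary supplies S only.

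**Enumeration** over four example sizes and three functional states (size-only grade → table grade):

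| Size | No interference | Interferes | Prevents daily activity |
|---|---|---|---|
| 1 cm | 0 → 0 | 0 → 2 | 0 → 3 |
| 3 cm | 1 → 1 | 1 → 2 | 1 → 3 |
| 7 cm | 2 → 2 | 2 → 2 | 2 → 3 |
| 12 cm | 3 → 3 | 3 → 3 | 3 → 3 |

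The size-only grade is too low in 5 of the 12 cells. In 3 of those 5 (activity prevented at 1, 3 or 7 cm) it falls below Grade 3, the grade needed for an induration event of special interest. Above 10 cm nothing is lost. The shortfall is one to three grades.

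These cells show what can happen, not how often. The planned number of diary cards is 198 × 3 = 594, but the documents do not say what share would record swelling that limits activity, so no count is offered.

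**Halting rule.** Section 7.3.2 counts subjects, and at full enrolment one third is 198 / 3 = 66. Nothing in the documents suggests that missed swelling events would decide whether that number is reached.

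**The case against.** The strongest reply is that the diary does not set the grade. Section 6.7 instructs the investigator to use the table, functional criteria included, and Section 7.1.5 says the same. Staff go through the diary with the subject at the 8 to 14 day call and again at the next in-person visit. The call also lists an injection-site reaction evaluation of its own, and staff decide then whether an office visit is needed. Section 6.3.3.10 provides for a final grade that differs from the diary entry, with the reason recorded. Subjects are told to report any event at once, and the Day 6 page asks them to tell the site about unresolved symptoms. Events are analysed from the adverse event form, to which the diary is one input.

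This largely stands. A reader might infer that activity-limiting swelling is systematically under-graded; the documents do not support that, because it would require grading from the centimetres alone and no section says so. Nor does the error run strictly one way, since the card tells subjects to choose the larger circle when the area lies between two. The event-of-special-interest definition also requires relatedness and persistence.

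The reply does not remove the gap. Permission to correct a grade does not supply the missing observation. The pain boxes may alert the reviewer but do not attribute the limitation to swelling, and the free-text field is for symptoms not already listed, while swelling is listed.

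**Conclusion.** The mismatch is real, and its consequence is a recall risk. The functional half of the swelling grade is not collected in the diary or prompted at its review, so swelling of 10 cm or less that limits activity can be graded too low and a Grade 3 induration event of special interest can be missed for an individual subject. By rule, the possible error is one to three grades; its frequency is unknown.

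A reader might infer a distorted trial-level safety profile or a weakened halting rule. Neither is shown: no frequency is given, and 66 subjects would be needed at full enrolment.

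The conclusion assumes that the card seen is still in use. It is stated to be unchanged at version 4.0, and the version 5.0 change list is silent on it, but the version 5.0 card cannot be checked. This is a worthwhile improvement in data capture for a secondary safety endpoint, not a flaw in the analysis.

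**What to change.** Under swelling on each diary page, add one line with three boxes in the grading table's own terms: did not interfere with activity, interfered with activity, prevented daily activity. Add the same item to the list in Section 6.3.3.10. At the existing diary review, have staff confirm the answer with the subject, including how long the limitation lasted. Version 5.0 ties daily activity to an impact of 24 hours, with the footnote marked on the pain row, and a daily tick alone would not establish that duration. The document should also say whether that definition applies to the swelling row.

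The cost is a revised and re-translated card and one extra tick per diary day. No new visit or procedure is needed, and the grading table itself does not change.
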